Title: Effects of Catheter Location on Postoperative Analgesia for Continuous Adductor Canal and Popliteal-Sciatic Nerve Blocks

Clinicaltrials.gov: NCT02523235

Date (text originally created): June 28, 2015

Date (document compiled from previously-created documents): July 22, 2019

RESEARCH DESIGN AND METHODS

This will be a single-center (UCSD), randomized, controlled investigation.

Enrollment. Consenting adults undergoing knee arthroplasty or foot/ankle surgery with a planned adductor canal or popliteal perineural catheter, respectively, will be offered enrollment. Study inclusion will be proposed to eligible patients prior to surgery. If a patient desires study participation, written, informed consent will be obtained using a current UCSD IRB-approved ICF. Selection for inclusion will not be based on gender, race, or socioeconomic status. Inclusion and exclusion criteria are listed in section #10 below.

Preoperative Procedures. Following written, informed consent, we will record baseline anthropomorphic information (age, sex, height, and weight) that is already provided by all patients having surgery. All subjects will have a peripheral intravenous (IV) catheter inserted, standard noninvasive monitors applied, supplemental oxygen administered via a nasal cannula or face mask, and positioned supine (adductor canal) or prone (popliteal-sciatic). Midazolam and fentanyl (IV) will be titrated for patient comfort, while ensuring that patients remain responsive to verbal cues. The area that will be subsequently covered by the catheter dressing will be clipped of hair, if necessary. The ultrasound will be placed to visualize the short axis (cross-section) of the adductor canal or popliteal regional at both proximal and distal locations. If both sites are acceptable for catheter insertion, the subject will be randomized using a computer-generated list (blocks of 8) to one of two treatment groups in a 1:1 ratio using sealed, opaque, consecutively numbered envelopes stratified by catheter type (adductor canal vs. popliteal-sciatic): (1) proximal vs (2) distal insertion.

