A 40 mL bolus of normal saline or lidocaine 2% with 1:400,000 of epinephrine will then be given through the needle. A flexible non-stimulating perineural catheter (FlexTip, Arrow International, Reading, PA, USA) will be inserted 3-5 cm past the needle tip; and the needle withdrawn over the catheter. If saline was administered pre-operatively, then the 40 mL of lidocaine 2% with 1:400,000 of epinephrine will be administered through the catheter following surgery. A "successful" catheter insertion will be defined as decrease in cutaneous sensation to cold on the plantar aspect of the foot.

Intraop: Patients may receive a general and/or neuraxial anesthetic that would be determined by the intraoperative anesthesia provider. Additional boluses of 10 mL 2% lidocaine with epinephrine may be given, if needed, via the perineural catheter.

Perineural infusion: An infusion pump will be attached to each subject's perineural catheter. The pump will provide ropivacaine 0.2% at 8 mL/h (adductor) or 6 mL/h (popliteal) basal rate infusion and a 4 mL patient-controlled bolus with a 30 minute lockout (all standard at UCSD).

Data collection: All data collection will be through standard UCSD nursing/therapy EPIC notes (adductor canal) or postoperative phone calls (popliteal) for the day following surgery.

Primary endpoint: The primary endpoint will be the average pain on post operative day 1 following surgery as measured on a numeric rating scale (0-10, 0=no pain, 10=worst imaginable pain) during the time periods of 08:00-24:00 (adductor) or the two hours preceding the data-collection phone call (popliteal).

Secondary endpoints: Popliteal subjects will be called the day following surgery to collect information regarding surgical pain (Numeric Rating Scale of 0 to 10, with "0" being no pain and "10" being the worst pain ever experienced), analgesic use (oral, IV, and infusion boluses), infusion side effects, and distance ambulated (adductor catheters only). Popliteal subjects will be called one week (+/- 1 day) following surgery to inquire about possible block-related complications.

Sample size estimates:

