Adductor canal. The primary analysis will utilize the Wilcoxon Rank Sum test. The figure below shows the estimated density of post-op day 1 pain scores following Proximal insertion (mean = 4.12, SD = 1.74) based on published data.¹⁰ To simulate power, we used the truncated Gaussian distribution with range 0 to 10; SD=1.74; Proximal group mean = 4.12; and Distal group means = 5, 5.5, 6, 6.5, 7, 6.5, and 8.

Under these assumptions and two-sided $\alpha = 5\%$, we simulated 10,000 trials with sample size of 25 per group with a primary end point measurement.

We found the simulated power to be as plotted below.

So we have 80% power to detect group differences in pain as small as about 1.52.

Popliteal-sciatic. Using an expected NRS mean=2.6 and SD=2.1 of average pain on postoperative day 1 (based on unpublished data from IRB study #101282), approximately 31 subjects in each treatment arm with a primary end point measurement will be required to detect a difference between treatment group means of 1.5. This is with a 2-sided alpha=0.05, beta=0.2, and power=0.8 (ClinCalc.com accessed June 28, 2015). We will employ a t-test for parametric data and Wilcoxon Rank Sum test for non-parametric data.

With the two locations combined, we will need 112 subjects with a primary end point measurement; and, we will enroll up to 150 subjects to account for drop-outs and subjects without a primary end point measurement.

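### Does the unset clock time of the popliteal day-1 call undermine that stratum's primary endpoint or its 80% power?

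*Combined protocol and SAP*

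**What the plan says.** All references are to the combined protocol and SAP.

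- **Primary endpoint.** Day-1 pain on a 0-10 scale is averaged "during the time periods of 08:00-24:00 (adductor") for knee patients and over "the two hours preceding the data-collection phone call (popliteal") for foot and ankle patients. The scale is anchored "0=no pain, 10=worst imaginable pain".
- **Secondary endpoints.** "Popliteal subjects will be called the day following surgery to collect information regarding surgical pain"; no hour is given. The later safety call does carry a tolerance: "Popliteal subjects will be called one week (+/- 1 day) following surgery". Here the top of the pain scale is worded as the worst pain the subject has ever had, not the worst imaginable.
- **Research design and methods.** "This will be a single-center (UCSD), randomized, controlled investigation". Under Preoperative Procedures, allocation is 1:1 in blocks of 8, by sealed opaque envelopes, stratified by catheter type. The supplied text does not mention masking.
- **Sample size estimates, Popliteal-sciatic.** "Using an expected NRS mean=2.6 and SD=2.1 of average pain on postoperative day 1 (based on unpublished data from IRB study #101282"), giving about 31 per arm to detect 1.5 points with 80% power at two-sided 5%. The analysis is a t-test or a Wilcoxon rank sum test.
- **Combined total.** 112 evaluable subjects are needed, and "we will enroll up to 150 subjects to account for drop-outs and subjects without a primary end point measurement".

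**The concern.** The hour of the call decides which two hours are scored. A morning call and an evening call on day 1 both comply, but they may catch a subject at different distances from the block. The adductor endpoint has clock limits and the one-week call has a tolerance; the call that produces a primary endpoint has neither. If call time drifted with treatment arm, the comparison would mix catheter location with time of day, and no stated masking rules that out.

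The second worry is power. If SD 2.1 came from a whole-day average and a two-hour score is more variable, 31 per arm would be too few. The stratum has little slack, so the origin of that SD seems important. The two top anchors add to the impression of a loosely specified outcome.

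**Working it through.** **1. Reproduce the plan's figure.** Inputs from Sample size estimates, Popliteal-sciatic: difference 1.5, SD 2.1, two-sided alpha 0.05, power 0.80, equal arms.

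n per arm = 2 × (1.960 + 0.842)² × (2.1 / 1.5)² = 2 × 7.849 × 1.96 = 30.8, rounded up to **31**.

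Power at 31 per arm: 1.5 / (2.1 × √(2/31)) = 1.5 / 0.533 = 2.812; 2.812 − 1.960 = 0.852; Φ(0.852) = **80.3%**.

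The noncentral t gives 79.0% at 31 and an n of 31.76, so 32. The plan says approximately 31, and both methods agree with that. The total also checks: 2 × 25 + 2 × 31 = 112.

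**2. How far the result depends on the SD.** Difference 1.5, 31 per arm. Only 2.1 is documented for this stratum. The 1.74 is the plan's adductor SD, shown for scale; the other values are assumptions.

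| SD | Power, normal | Power, noncentral t | n per arm for 80% (normal) |
|---|---|---|---|
| 1.74 | 92.4% | 91.6% | 22 |
| 2.0 | 84.0% | 82.8% | 28 |
| 2.1 | 80.3% | 79.0% | 31 |
| 2.2 | 76.6% | 75.2% | 34 |
| 2.3 | 72.8% | 71.4% | 37 |
| 2.5 | 65.6% | 64.2% | 44 |

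The largest SD that keeps 80% is 1.5 / (2.802 × √(2/31)) = 2.11 by the normal approximation, or 2.07 by the noncentral t. Any trial sized for 80% sits at such an edge, so the table alone does not show a mistake.

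**3. What variable call times could cost.** Suppose SD 2.1 excludes call-time variation and that variation adds an independent SD of s (assumed). The total SD is √(2.1² + s²).

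- s = 0.5: √4.66 = 2.16, power 78.1%.
- s = 1.0: √5.41 = 2.33, power 71.9%.

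If the source scores were also collected by calls without a fixed hour, this variation is already inside 2.1 and nothing is lost. The document does not say which.

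**4. Bias.** Suppose mean pain changes by b points per hour of call time, and mean call time differs by d hours between arms. The bias is then about b × d. Randomisation with one call procedure gives an expected d of zero, whatever b is. The document gives no value for either and no mechanism that would make d differ from zero. If the catheter effect itself varies over the day, the comparison estimates its average over the call times used, which is still a valid contrast.

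**5. Does the SD belong to the endpoint?** The sample-size paragraph describes its source data in nearly the same phrase that the Primary endpoint section uses for the outcome. That does not prove a two-hour recall, because the phrase also covers the adductor window. It leans towards a match, and nothing in the text points the other way.

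**The case for a change.** The best opposing case is that call time is part of the endpoint's definition, that the protocol sets windows elsewhere, and that a window and a sentence on the SD's origin would cost little. Subjects and callers may know the allocation, and call time is settled after randomisation. The popliteal stratum is 62 of the 112 required subjects and has its own powered comparison.

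It stands that the hour is unstated, the recall period behind SD 2.1 is unstated, and the anchors differ. Less of the rest survives:

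- The silence on masking is weak evidence. The file was compiled from earlier documents and points to a section 10 that is not in the supplied text.
- The adductor window spans 16 hours (08:00 to 24:00), so it is not a tight standard against which the popliteal call falls short.
- A clock window would not equalise time since the block, because the Popliteal-sciatic section lets the lidocaine bolus be given before or after surgery.
- Planning for a larger SD is not free. At SD 2.3 the t-test needs 38 per arm: 76 + 50 = 126 in total, leaving 24 of 150 places (16%) for losses. At SD 2.5 it needs 45 per arm: 90 + 50 = 140, leaving 10 (7%). The plan now leaves 38 (25%). Giving that up for an assumed SD is hard to defend.
- The anchor wording would reach both arms alike, so it has no shown effect on the difference between them.

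**Conclusion.** No change to the plan follows. The unstated hour is a gap that staff fill with a routine call schedule applied to everyone; noting the time of each call is ordinary practice and would let an analyst describe timing by arm. The two anchors are a clerical slip. On power there is no demonstrated error: 31 per arm gives 80.3% (79.0% by noncentral t) at the only SD documented for this stratum, and the text supports neither a larger nor a smaller one.

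This rests on two assumptions: that call timing does not depend on arm, and that SD 2.1 describes the outcome named in nearly the same words. If the second failed, power could move either way: 82.8% at an assumed SD of 2.0, 71.4% at 2.3 (noncentral t). That would affect precision in the popliteal stratum only. It would not invalidate the comparison or touch the adductor stratum.
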